3. ABSTRACT

Title

Characterising the use of JAK inhibitors in Europe: a Drug Utilisation Study

Rationale and background

JAKi therapy has been gaining popularity for the treatment of several autoimmune conditions, including rheumatoid arthritis, inflammatory bowel disease, and atopic dermatitis. The first JAKi, tofacitinib, was approved by the European Medicines Agency (EMA) for the management of rheumatoid arthritis in 2017. An FDA-requested study (the Oral Rheumatoid Arthritics Trial (ORAL) Surveillance trial) showed a higher risk of major adverse cardiovascular events (MACE), cancer and adjudicated opportunistic infection with tofacitinib compared to tumour necrosis factor (TNF) inhibitors in patients aged 50 years or older with at least one cardiovascular risk factor. Further research has been conducted on the safety profile of JAKi for other indications, including psoriatic arthritis, ulcerative colitis and atopic dermatitis. It was shown that risk of venous thrombotic events of JAKi users was similar to placebo users in patients with atopic dermatitis and ulcerative colitis. Incidence of adverse events, including herpes zoster infection and thrombotic events, remained similar with longer follow-up up to two years in psoriatic arthritis patients with JAKi. However, especially in these newer indications, the available evidence has been limited by short duration of follow-up and limited sample size.

The current study aims to identify the incidence of new JAKi use over time, and to characterise new users of JAKi in Europe to inform the feasibility of future safety studies.

Research question and objectives

This study aims to characterise the use of JAKi in Europe.

The specific objectives are:

- 1. To estimate the incidence of new JAKi use, overall and for each individual JAKi ingredient.
- 2. To characterise new JAKi users and treatment for each individual JAKi ingredient, over all indications and stratified by indication.

Methods

Study design

- Population level cohort study (objective 1)
- New user cohort study (objectives 2)

Population

The population level cohort study will include all subjects available in the selected databases from 1st January 2017 until the most recent data lock of their respective databases, with at least 365 days of data visibility.

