7. RESEARCH QUESTION AND OBJECTIVES

Table 1. Primary and secondary research questions and objective.

A. Objective 1. Population-level drug utilisation

Objective 1:	To estimate the incidence of new JAKi use, overall and for each individual JAKi ingredient	
Hypothesis:	Not applicable	
Population (mention key inclusion- exclusion criteria):	The study includes all people available in the databases with at least 365 days of data visibility.	
Exposure:	Not applicable	
Comparator:	Not applicable	
Outcome:	JAKi (abrocitinib, filgotinib, baricitinib, upadacitinib, tofacitinib)	
Time (when follow up begins and ends):	From 1 st January 2017 until the most recent data lock for each included database.	
Setting:	Data will be collected from primary care and secondary care outpatient setting with the following databases:	
	- FinOMOP-HILMO (primary care, secondary care outpatient)	
	- IPCI (primary care)	
	- IQVIA DA Germany (primary care)	
	- NLHR (primary care, secondary care outpatient)	
	- VID (primary care, secondary care outpatient)	
Main measure of effect:	Annual incidence rates of JAKi use, for the entire class pooled together and for each JAKi ingredient	

B. Objectives 2. Patient-level characterisation and drug utilisation studies

Objective 2:	To characterise new JAKi users and treatment, overall and stratified by ingredient and indication	
Hypothesis:	Not applicable	
Population (mention key inclusion- exclusion criteria):	The study includes all patients available in the databases initiating JAKi therapy, with at least 365 days of data visibility before therapy initiation	
Exposure:	JAKi (abrocitinib, filgotinib, baricitinib, upadacitinib, tofacitinib)	
Comparator:	Not available	
Outcome:	Not available	
Time (when follow up begins and ends):	For treatment characterisation: from each JAKi therapy initiation until the discontinuation of index drug	
Setting:	Data will be collected from primary care and secondary care outpatient setting with the following databases: - FinOMOP-HILMO (primary care, secondary care outpatient)	

DARWIN M	P3-C1-001 Study Protocol	
○EU/V	Author(s): [name], [name]	Version: V3.0
,		Dissemination level: Public

	 IPCI (primary care) IQVIA DA Germany (primary care) NLHR (primary care, secondary care outpatient) VID (primary care, secondary care outpatient)

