8.2 Study setting and data sources

This study will be conducted using 5 databases onboarded for DARWIN EU® network of data partners from 5 European countries. These databases have been selected based on geographic representativeness and availability of data on JAK inhibitors. The selected databases cover Finland, Germany, Norway, The Netherlands and Spain. The results generated from these databases will therefore cover regions of Northern, Central and Southern Europe.

Detailed information of the selected data sources is described in Table 3.

Author(s): [name], [name]

Version: V3.0

Dissemination level: Public

Table 3. Description of the selected data sources.

Country	Name of Database	Justification for Inclusion	Health Care setting	Type of Data)	Number of active subjects	Feasibility count of exposure ¹	Data lock for the last update
Finland	FinOMOP-	Databases include adequate	Drimany care CD primary	EHR,	6.25M	2500	2024-04-16
rinianu	HILMO	Databases include adequate number of records of JAK inhibitors for subsequent patient characterisation.	Primary care GP, primary care specialist, secondary care specialist, hospital inpatient care	registries	6.23IVI	2500	2024-04-16
The Netherlands	IPCI	Databases include adequate number of records of JAK inhibitors for subsequent patient characterisation.	Primary care GP	EHR	1.25M	700	2024-04-30
Germany	IQVIA DA Germany	Databases include adequate number of records of JAK inhibitors for subsequent patient characterisation.	Primary care GP, primary care specialist	EHR	4.35M	7900	2023-09-30
Norway	NLHR	Databases include adequate number of records of JAK inhibitors for subsequent patient characterisation.	Primary care GP, primary care specialist, secondary care specialist, hospital inpatient care	Registries	5.74M	2600	2024-06-30
Spain	VID ²	Databases include adequate number of records of JAK inhibitors for subsequent patient characterisation.	Primary care GP, secondary care specialist, hospital inpatient care, nursing homes	EHR, registries	1.61M	600	2022-01-01

^{1.} Feasibility count of exposure was identified as unique exposed individuals.

^{2.} Only female individuals are included in this data source.

P3-0	1-00	11 Sti	ıdv Pr	otocol

Version: V3.0

Dissemination level: Public

Information on data sources used is described below:

Finnish Care Register for Health Care [FinOMOP-HILMO] (Finland)

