The Valencia Health System Integrated Dataset (VID) is a set of multiple, public, population-wide electronic databases for the Valencia Region, the fourth most populated Spanish region, with about 5 million inhabitants and an annual birth cohort of 48 000 newborns, representing 10.7% of the Spanish population and around 1% of the European population. The VID provides exhaustive longitudinal information including sociodemographic and administrative data (sex, age, nationality, etc.), clinical (diagnoses, procedures, diagnostic tests, imaging, etc.), pharmaceutical (prescription, dispensing) and healthcare utilisation data from hospital care, emergency departments, specialised care (including mental and obstetrics care), primary care and other public health services. It also includes a set of associated population databases and registries of significant care areas such as cancer, rare diseases, vaccines, congenital anomalies, microbiology (including COVID-19 test results registry) and others, and also public health databases from the population screening programmes. All the information in the VID databases can be linked at the individual level through a single personal identification code. The databases were initiated at different moments in time, but all in all the VID provides comprehensive individual-level data fed by all the databases from 2008 to date. The OMOP instance has been created using CONSIGN project data, where 1.96 million of females in fertile age are studied from start of 2018 to end of 2021.

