8.3 Study period

The study period starts from 1st January 2017 until the most recent data lock for each included database (see **Table 3**).

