8.6 Variables

8.6.1 Exposure/s

In the population level DUS (Objective 1) no exposure variable will be defined. The incident use of JAKi will be the outcome in the analyses, as described in section 8.6.2 below.

Exposure of interest in the characterization of JAKi initiators (Objective 2) will be the initiation of treatment with the following JAKi, including abrocitinib, filgotinib, baricitinib, upadacitinib, and tofacitinib. Operational definition of exposure is described in **Table 4**.

Author(s): [name], [name]

Version: V3.0

Dissemination level: Public

Table 4. Operational definitions of exposure.

Exposure group name(s)	Details	Washout window	Assessment Window	Care Setting ¹	Code Type	Applied to study populations	Incident with respect to	Measurement characteristics / validation	Source of algorithm
Individual JAKi ingredient	Preliminary code lists provided in Appendix I.	[-Inf, -1]	First ever exposure of each individual JAKi ingredient will be assessed during the study period of 2017-2024.	ОР	RxNorm	For patient level characterization (objective 2)	Specific individual JAKi ingredient	N/A	N/A

¹ IP = inpatient, OP = outpatient, ED = emergency department, OT = other, n/a = not applicable

P3-C1-001 Stud	dy Protocol
----------------	-------------

Version: V3.0

Dissemination level: Public

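### VID holds only women of fertile age (2018-2021), but the plan treats it like the other databases: its crude rate has no counterpart elsewhere and the Southern Europe claim is too broad

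*Protocol*

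**What the plan says.** The description of VID in Section 8.2 of the protocol limits the OMOP instance by sex, age and calendar time: "1.96 million of females in fertile age are studied from start of 2018 to end of 2021". Footnote 2 to Table 3 repeats only the sex limit: "Only female individuals are included in this data source". The age limits of the fertile-age group are not given anywhere.

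The design text makes no exception for VID:

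- Abstract: "The population level cohort study will include all subjects available in the selected databases from 1st January 2017 until the most recent data lock".
- Section 8.3: "The study period starts from 1st January 2017 until the most recent data lock for each included database".
- Section 8.6.1, Table 4: "First ever exposure of each individual JAKi ingredient will be assessed during the study period of 2017-2024". Table 3 gives the VID lock as 2022-01-01.
- Section 7, Table 1, main measure for Objective 1: "Annual incidence rates of JAKi use, for the entire class pooled together and for each JAKi ingredient".

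Stratification, listed in the Abstract, is by ingredient and indication only. Section 8.8.2 describes no age or sex strata and no standardisation for incidence.

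On the choice of databases, Section 8.2 says: "These databases have been selected based on geographic representativeness and availability of data on JAK inhibitors". It then concludes: "The results generated from these databases will therefore cover regions of Northern, Central and Southern Europe". VID is the only Spanish source and the only one in Southern Europe. Section 11 gives one database-specific denominator caveat, for IQVIA DA Germany, and none for VID.

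**The concern.** A crude rate depends on the age and sex mix of its denominator. In four databases that mix is people of all ages and both sexes. In VID it is women within an unstated age band. The report will show a Spanish series in the same format as the other four, with no rate from another country for the same kind of women. A reader cannot tell how much of any gap reflects JAKi use and how much reflects the way the extract was built.

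The stated purpose is to inform the feasibility of future safety studies. The background cites a safety signal in patients aged 50 or older with a cardiovascular risk factor. A planner who takes the coverage sentence at face value would assume that Southern European men and older patients are represented. In Objective 2, sex has a single value in VID, and the 0-3 and over-60 age bands should be empty or nearly so, depending on the missing age limits.

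**Working it through.** The protocol gives no precision or sample-size figure for incidence, so there is nothing of its own to reproduce. The checks below use its population counts and dates.

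**1. Share of the region that VID covers.** Inputs from Section 8.2: 1.61 million active subjects (Table 3), 1.96 million women studied (VID text), about 5 million inhabitants of the Valencia region (VID text).

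- 1.61 / 5 = 0.322
- 1.96 / 5 = 0.392

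That is about 32% to 39%. The 1.96 million may be a cumulative count over the four years, so the lower figure may be the better guide to a single year.

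**2. When the VID rate equals the regional rate.** Let w be the share of regional person-time held by women of fertile age, and R the initiation rate in everyone else divided by the rate in those women. Then

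whole-population rate / VID rate = w + (1 - w) × R.

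This equals 1 only when R = 1. The documents give no value for R, so the table is an illustration over assumed values:

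| R (assumed) | w = 0.322 | w = 0.392 |
|---|---|---|
| 0.5 | 0.66 | 0.70 |
| 1 | 1.00 | 1.00 |
| 1.5 | 1.34 | 1.30 |
| 2 | 1.68 | 1.61 |
| 3 | 2.36 | 2.22 |

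For example, with w = 0.322 and R = 2: 0.322 + 0.678 × 2 = 1.68. Both the size and the direction depend on R.

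**3. Calendar window.** From 1 January 2017 to the locks in Table 3, the nominal spans are 5.0 years for VID, 7.3 for FinOMOP-HILMO, 7.3 for IPCI, 6.7 for IQVIA DA Germany and 7.5 for NLHR. If VID observation begins on 1 January 2018, its data span 4.0 years. Section 8.4 lets person-time start only after 365 days of visibility, and 1 January 2018 + 365 days = 1 January 2019. That leaves about 3.0 years, 2019 to 2021. VID would then give no rate for 2017 or 2018, and its lock rules out any rate after 2021.

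**4. Is a matching rate planned elsewhere?** No. Age and sex are variables for patient characterisation in Objective 2 (Section 8.6.3). They are not strata for Objective 1.

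**The case against.** The strongest reply is that the restriction is disclosed and little follows from it. Section 8.2 gives the sex, the age group and the years. Section 8.5 includes whoever is available in each database, which for VID means the women it holds, and Section 8.3 refers to Table 3 for each lock. A reader might infer that the protocol claims men are in the VID denominator; it does not. This part of the reply stands. But the footnote omits the age limit and the 2018 start, and neither restriction reaches the population, period or limitations text.

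The follow-up rule in Section 8.4 removes ineligible person-time without further instruction. A reader might infer that VID rates for 2017 and 2018 would be biased; under that rule they would be missing. Nor is a start on 1 January 2019 a stated fact. The VID text also says that the source databases hold individual-level data from 2008, and it does not say whether earlier observation time was loaded into the OMOP instance.

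Sections 8.8 and 8.9 analyse and present each database separately, with no meta-analysis. The pooling mentioned in Table 1 is across JAKi, not across databases. A reader might infer a formal Spanish comparison or a pooled European rate; neither is planned. The harm is confined to side-by-side reading and the coverage sentence.

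Finally, the feasibility counts per 100,000 active subjects look similar: VID 37.3 (600 / 1.61 million), Finland 40.0, Norway 45.3, Netherlands 56.0, with Germany at 181.6. These are counts of people ever exposed, from databases with different locks, and they are not annual rates. They cannot show that the VID rate stands for a general population. The spread does support one part of the objection: care setting differs between databases, and age-sex strata will not remove that.

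**Conclusion.** The point holds as a mismatch of population and an overbroad coverage claim. The VID crude rate is a rate for women of fertile age, covering about 32-39% of the region's inhabitants. It is not the quantity reported for the other four databases, and nothing in the plan supplies a like-for-like rate.

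A reader might go further and put a figure or a sign on the bias. The documents do not support that: the initiation rate outside the fertile-age group is unknown, and the table above moves from below 1 to above 2 on assumed values alone. The loss of 2017 and 2018 is conditional on VID observation starting on 1 January 2018.

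This should be corrected before results are presented. It does not undermine the other four databases, and the count of exposed women in VID remains usable for feasibility if it is labelled as such.

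**What to change.** - In Sections 8.3 and 8.5, state the VID population (female, with the actual age limits) and the observation window actually loaded, including whether any time before 2018 is available. Align the period in Table 4 with it.
- In Section 11, add a VID limitation alongside the one for IQVIA DA Germany.
- In Section 8.2, limit the Southern Europe statement to women of fertile age in the Valencia region.
- In Section 8.8.2, add to Objective 1 at least one incidence stratum in the other four databases: women within the same age limits, over the calendar years that overlap with VID. Name it as the only rate to be read beside VID. Full sex-by-age stratification is optional.

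The cost is low: the text edits, plus sex and age settings in an analysis that already holds both variables. The drawbacks are some extra small cells, already masked when below 5 under Section 8.8, and a narrower coverage claim. Differences in care setting will remain and should be stated when the rates are read together.

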8.3 Study period

The study period starts from 1st January 2017 until the most recent data lock for each included database (see **Table 3**).

8.4 Follow-up

For the population-level drug utilisation study (objective 1), eligible study participants will begin to contribute person time from the latest of the following: (1) study start date, (2) date at which the observation period starts (i.e. 1st January of each year), or (3) date with at least 365 days of data visibility. Respective study participants will stop contribute person time at the earliest date of the following: (1) date on which the observation period ends (i.e. 31st December of each year), (2) end of data availability, or (3) date of first JAKi exposure if applicable (outcome of the incidence analysis).

For patient-level characterisation (objectives 2), eligible study participants with at least 365 days of data visibility will be follow-up from the date of first JAKi exposure until the earliest of (1) end of index JAKi treatment exposure, (2) death, (3) loss to follow-up, or (4) end of data availability.

[figure not shown]

Figure 1. HARPER diagram for index date definition in population level DUS (Objective 1).

- (a) Exposure of interest: any JAKi, individual JAKi ingredient
- (b) Earliest of: 31st December of each year, loss of follow-up, end of data availability, initiation of exposure of interest

Cohort Entry Date First exposure of interesta Day 0 **Washout Window** (No exposure of interesta) Days [- ∞, -1] **Data Visibility** Days [-365, -1] **Covariate Assessment Window** (Age, sex) Days [0, 0] **Covariate Assessment Window** (Indication) Days [-∞, -1] mmmmmFollow up Window Days [0, censor^b]

Figure 2. HARPER diagram for index date definition in patient level characterization (Objective 2).

- (a) Exposure of interest: individual JAKi ingredient
- (b) Earliest of: end of treatment with index exposure of interest, death, loss to follow-up, end of data availability

Time

P3-0	1-00	11 Sti	ıdv Pr	otocol

Version: V3.0

Dissemination level: Public

8.5 Study population with inclusion and exclusion criteria

For population level DUS (Objective 1)

All individuals available in the respective databases from 1st January 2017 until the end of data availability, with at least 365 days of data visibility, will be included in the population level DUS.

Different exclusion criteria will be applied corresponding to each outcome of the JAKi exposure incidence rate analysis (as defined in section 8.6.2). For incidence of first JAKi ever initiation, individuals with any JAKi exposure before index date will be excluded. For incidence of individual JAKi ingredient (abrocitinib/filgotinib/upadacitinib/tofacitinib) initiation, individuals with respective JAKi exposure before index date will be excluded.

For patient level characterization (Objectives 2)

All individuals available in the respective databases from 1st January 2017 until the end of data availability, that newly initiated JAKi and at least 365 days of data visibility, will be included in the patient level DUS. Individuals with specific JAKi exposure before the start of study period (i.e. 1st January 2017) will be excluded.

8.6 Variables

8.6.1 Exposure/s

In the population level DUS (Objective 1) no exposure variable will be defined. The incident use of JAKi will be the outcome in the analyses, as described in section 8.6.2 below.

Exposure of interest in the characterization of JAKi initiators (Objective 2) will be the initiation of treatment with the following JAKi, including abrocitinib, filgotinib, baricitinib, upadacitinib, and tofacitinib. Operational definition of exposure is described in **Table 4**.

Author(s): [name], [name]

Version: V3.0

Dissemination level: Public

Table 4. Operational definitions of exposure.

Exposure group name(s)	Details	Washout window	Assessment Window	Care Setting ¹	Code Type	Applied to study populations	Incident with respect to	Measurement characteristics / validation	Source of algorithm
Individual JAKi ingredient	Preliminary code lists provided in Appendix I.	[-Inf, -1]	First ever exposure of each individual JAKi ingredient will be assessed during the study period of 2017-2024.	ОР	RxNorm	For patient level characterization (objective 2)	Specific individual JAKi ingredient	N/A	N/A

¹ IP = inpatient, OP = outpatient, ED = emergency department, OT = other, n/a = not applicable

P3-C1-001 Stud	dy Protocol
----------------	-------------

Version: V3.0

Dissemination level: Public

8.6.2 Outcome/s

In the population level DUS (Objective 1), the incident use of JAKi will be the outcome in the analyses.

For the incidence of first JAKi ever initiation, the outcome will be defined as first prescription/dispensation of any JAKi. For incidence of individual JAKi ingredient (abrocitinib/ baricitinib/ filgotinib/ tofacitinib/ upadacitinib) initiation, the outcome will be defined as first prescription/dispensation of respective individual JAKi ingredient.

8.6.3 Other covariates, including confounders, effect modifiers and other variables

The following covariates will be reported as part of patient and treatment characterisation for each specific individual JAKi ingredient.

- Age at index date will be calculated. Age will be presented as a mean/median age as well as proportion of patient stratified within age groups (0-3, 4-12, 13-18, 19-40, 41-60, >60).
- Sex (male/female)
- Pre-specified indicated condition for JAKi, defined by condition recorded before index date (yes/no for each indication). Indications of JAKi will be defined by any records of the above-mentioned prespecified conditions before the first exposure of specific individual JAKi ingredient. Multiple indications are allowed. Preliminary code lists for the pre-defined indications are provided in Appendix I.
 - Atopic dermatitis
 - Juvenile idiopathic arthritis
 - o Inflammatory bowel disease
 - o Alopecia areata
 - Axial spondyloarthritis
 - Psoriatic arthritis
 - Rheumatoid arthritis
 - Unknown indication (defined as none of the predefined indications were found)
- Time from first indication to first JAKi initiation, estimated separately for each pre-specified indication (more than one per patient is possible) and presented in months
- Duration of index JAKi treatment era (months)
- Prior use of other JAKi (yes/no)

In addition, a large-scale characterisation for identifying potentially missing diagnosis codes from prespecified lists will be performed.

The following covariates will be used for the stratification in patient characterisation.

- Pre-defined indication

The study covariates are described conceptually, and the context or rationale for the choices are provided in this section. The operational definition of the covariates is described in the **Table 5**.

Author(s): [name], [name]

Version: V3.0

Dissemination level: Public

Table 5. Operational definitions of covariates.

Characteristic	Details	Type of variable	Assessment window	Care Settings ¹	Code Type	Diagnosis Position ²	Applied to study populations	Measurement characteristics/validation	Source for algorithm
Age	Age at index date in years	Numeric, continuous	[0,0]	OP	N/A	N/A	individual JAKi ingredient	N/A	N/A
Sex	Biological sex as recorded	Binary, count	[0,0]	OP	N/A	N/A	individual JAKi ingredient	N/A	N/A
Indication	Diagnosis of pre-defined condition considered as possible indication for JAKi, including atopic dermatitis, juvenile idiopathic arthritis, inflammatory intestinal disease, alopecia areata, axial spondyloarthritis, psoriatic arthritis, rheumatoid arthritis and unknown indication	Binary, count	[-Inf, -1]	ОР	SNO MED	N/A	individual JAKi ingredient	N/A	N/A
Time from first diagnosis of indication to JAKi initiation	Time from first possible indication for JAKi to first exposure of each individual JAKi ingredient	Numeric, continuous	[-Inf, 0]	OP	N/A	N/A	individual JAKi ingredient	N/A	N/A
Treatment duration	Duration of JAKi used	Numeric, continuous	[0, end of index drug era]	OP	N/A	N/A	individual JAKi ingredient	N/A	N/A

¹IP = inpatient, OP = outpatient, ED = emergency department, OT = other, n/a = not applicable

² Specify whether a diagnosis code is required to be in the primary position (main reason for encounter)

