The database contains demographics records, basic medical data, disease diagnosis according to International Classification of Diseases, 10th revision (ICD-10), and prescription records. While the database partly records information on deaths and procedures, it currently does not support linkage with external data sources. Routine updates are conducted at regular intervals.

IQVIA DA Germany is suitable for pharmacoepidemiologic and pharmacoeconomic studies as previously demonstrated. The quality of data is assessed based on several criteria including completeness of information and correctness (e.g. linkage between diagnosis and prescriptions).

Norwegian Linked Health Registry data [NLHR] (Norway)

Norway has a universal public health care system consisting of primary and specialist health care services covering a population of approximately 5.4 million inhabitants. Many population-based health registries were established in the 1960s with use of unique personal identifiers facilitating linkage between registries. Data in these health registries are used for health analysis, health statistics, improving the quality of healthcare, research, administration and emergency preparedness. We harmonised data from the following registries: the Medical Birth Registry of Norway (MBRN), the Norwegian Prescription Registry (NorPD), the Norwegian Patient Registry (NPR), Norway Control and Payment of Health Reimbursement (KUHR), the Norwegian Surveillance System for Communicable Diseases (MSIS), the Norwegian Immunisation Registry (SYSVAK), the National Death Registry, and the National Registry (NR). Linkage between the registries was facilitated using project-specific person ID generated from unique personal identification assigned at birth or immigration for all legal residents in Norway. In brief: MBRN stores information about the pregnancy, the mother, father and child; NPR records diagnosis in secondary care (e.g., hospital); KUHR contains information about diagnosis and contact in primary care (e.g., GPs and outpatient specialists) – to be included in third release; NorPD recorded all medications dispensed outside of hospitals; MSIS collects test results of communicable diseases (e.g., Sars-Cov-2); SYSVAK recorded vaccinations.

Valencia Health System Integrated Dataset [VID] (Spain)

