11. LIMITATIONS OF THE RESEARCH METHODS

The study will be informed by routinely collected health care data and so data quality issues must be considered. In particular, a recording of a prescription or dispensation does not mean that the patient actually took the drug. In addition, assumptions around the duration of drug use will be unavoidable.

The actual reason for prescription of the drug is not recorded in any of the databases. We will assess indication via a proxy based on pre-defined conditions recorded on the date of therapy initiation. Therefore, recording of potential indication may be incomplete. In addition, the completeness of recordings of co-morbidities used for patient characterisation may variate across databases.

In IQVIA DA Germany, the observation period of the patients in these databases is calculated based on the last visit, observation or interaction of the patient with the health care system. This methodology impacts the individuals considered "at risk" for the different medicines of interest of the study (i.e., the individuals included in the denominator populations) during the latest months of available data from the latest data lock, where healthy and/or non-frequent users of the health care system will not be considered active. Consequently, the denominators that will be used to calculate the incident use of drugs in the population may present an artefactual decrease whilst the incident users will remain. The presence of these artefacts will be considered when interpreting the results.

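### The protocol defines indication by records up to the day before the first JAKi record, but Section 11 bases it on records of that day and Table 5 runs time from diagnosis to day 0; one window including day 0 is needed

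*Protocol*

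**What the plan says.** Four places in the protocol fix when a condition must be recorded to count as the indication, and a fifth depends on it.

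- Section 8.6.3, covariate list: "Pre-specified indicated condition for JAKi, defined by condition recorded before index date (yes/no for each indication".
- Section 8.6.3, next sentence: "Indications of JAKi will be defined by any records of the above-mentioned prespecified conditions before the first exposure of specific individual JAKi ingredient".
- Figure 2 (section 8.4) and the indication row of Table 5 (section 8.6.3): the assessment window is unlimited lookback to day -1.
- Section 11: "We will assess indication via a proxy based on pre-defined conditions recorded on the date of therapy initiation".
- Table 5, time-from-diagnosis row, described as "Time from first possible indication for JAKi to first exposure of each individual JAKi ingredient": the window is [-Inf, 0].

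The residual category is "Unknown indication (defined as none of the predefined indications were found".

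On care setting, the indication row of Table 5 carries the code OP, which the table footnote defines as outpatient. Table 3 lists hospital inpatient care for FinOMOP-HILMO, NLHR and VID, but not for IPCI or IQVIA DA Germany.

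**The concern.** Indication is the only stratifier that section 8.6.3 names for the patient characterisation. Section 14 promises age, time from diagnosis, treatment duration and prior use of other JAKi for each indication. The stated purpose is to inform the feasibility of later safety studies, and section 6 names small numbers in the newer indications as the obstacle. The count of users per indication is therefore a main product of the study.

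A diagnosis entered on the same day as the first JAKi record is the record closest in time to the treatment decision. The operational rule discards it, the limitations section says it is what will be used, and a neighbouring variable includes that day. Whoever writes or checks the code has conflicting statements to reconcile.

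**Working it through.** The plan gives no figure to reproduce, so the check applies each rule to the same patients. Let day 0 be the first exposure to the ingredient in question.

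**Rules**
- R1 (section 8.6.3, Figure 2, Table 5 indication row): records in [-Inf, -1].
- R2 (Section 11, read literally): records on day 0 only.
- R3 (Table 5 time-from-diagnosis row): records in [-Inf, 0].

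R1 and R2 share no day. R3 is their union.

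**Patients**

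| Records of listed conditions | R1 | R2, literal | R3 |
|---|---|---|---|
| Condition A before day 0 and again on day 0 | A | A | A |
| Condition A before day 0 only | A | not A | A |
| Condition A first on day 0, nothing else earlier | unknown | A | A, interval 0 months |
| Condition A first on day 0, condition B earlier | B only | A only | A and B |

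Row 2 shows that Section 11 cannot be meant literally, since it would drop everyone with only an earlier diagnosis. Row 3 is the patient who becomes unknown under the operational rule. Row 4 keeps an indication but loses A, although section 8.6.3 allows several per patient.

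**Direction.** R1 is nested in R3. Moving from R1 to R3 can only raise the count for each indication and can only lower the unknown count. The patients added have an interval of 0 months, so R1 also removes the zeros from the time-from-diagnosis distribution.

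**Dependence on ingredient.** The index date is specific to the ingredient. Suppose a patient in row 3 later starts a second JAKi. The code for A now precedes the second index date, so under R1 the patient is unknown for the first ingredient and A for the second, on the same diagnosis record.

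**Size.** The feasibility counts in section 8.7 sum to 2,500 + 700 + 7,900 + 2,600 + 600 = 14,300. The affected number is p times the eligible new users, where p is the share whose first record of a listed condition is on day 0; those who become unknown are the subset with no other listed condition earlier. The documents give neither p nor that subset. For scale only, p = 1% would be 0.01 × 14,300 = 143 people and p = 20% would be 0.20 × 14,300 = 2,860. Both shares are assumptions. The base is also approximate, because the counts are unique exposed people and not new users with 365 days of data visibility.

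**Care setting.** Inpatient codes exist only in FinOMOP-HILMO, NLHR and VID: 2,500 + 2,600 + 600 = 5,700 of the 14,300. The other 7,900 + 700 = 8,600 cannot be affected by an outpatient filter on diagnoses.

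**The case against.** The best defence is that the operational rule is clear. Section 8.6.3 states it twice, Figure 2 and Table 5 repeat it, and the text names Table 5 as the place for operational definitions. The odd one out is a descriptive sentence in the limitations. That makes it likely that the code would follow [-Inf, -1]. It does not remove the conflict, and it does not make a rule that discards day-0 records a good one. The admission in Section 11 that indication may be incompletely recorded concerns missing data, not records that are present and left out.

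It can also be said that an interval ending at initiation naturally has a window ending on day 0, and that a patient not classed under an indication would not appear in its time-from-diagnosis table. This is fair: an interval of 0 months for a patient labelled unknown is a possible reading of Table 5, not a stated output.

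A reader might infer several stronger points that the documents do not support.

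- **Everyone diagnosed on the prescribing day becomes unknown.** Lookback is unlimited, with at least 365 days of data visibility. A patient with an earlier record of the same condition is classified correctly, and one with an earlier record of another listed condition is placed under that one.
- **Same-visit coding is expected in IQVIA DA Germany.** Section 8.2 mentions "linkage between diagnosis and prescriptions" as an example of a data-quality criterion. It does not say that diagnoses are entered at the prescribing visit, or that such a code is the first.
- **All Objective 2 results are affected.** Age and sex are also reported for each ingredient over all indications, and those results do not depend on the window.
- **The outpatient code is part of the same contradiction.** Section 11 is silent on care setting, and OP agrees with the outpatient setting declared in Table 1. It also appears in the age and sex rows, where it can hardly act as a filter on records.

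**Conclusion.** The inconsistency stands on the protocol's own text. Followed as written, the indication rule omits a first qualifying diagnosis recorded on the index date. The patient is lost from that indication's count, and is labelled unknown only if no other listed condition was recorded earlier. The direction is certain relative to a window that includes day 0: indication counts are understated and the unknown group is overstated. The frequency of each indication and the indication-stratified results are affected; age and sex over all indications are not.

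The size cannot be estimated from the documents, and the scale figures above should not be read as an expected loss. Whether the effect differs between databases is likewise open.

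The care-setting question is separate and smaller. Section 8.6.3 admits any record while Table 5 says outpatient, and this can matter only in the three sources that list inpatient care.

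**What to change.** 1. Use one indication window that includes day 0, [-Inf, 0], in the section 8.6.3 text (both sentences), Figure 2 and the indication row of Table 5. It then matches the time-from-diagnosis row.
2. Reword the sentence in Section 11 to say that the proxy uses pre-defined conditions recorded on or before the date of therapy initiation.
3. Separately, reconcile the OP code in the indication row of Table 5 with the wider wording of section 8.6.3, by stating whether inpatient diagnoses count in FinOMOP-HILMO, NLHR and VID.

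The cost is one window parameter, a few edited lines and, if inpatient diagnoses are to count, one setting in the code. No new data are needed.
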